2. STATISTICAL HYPOTHESES

The primary objective of this study is to compare the rate of effective hemostasis between and exanet and UC group. The following hypothesis will be evaluated:

Ho:
$$\pi_{UC} - \pi_{andexanet} = 0$$

HA: $\pi_{UC} - \pi_{andexanet} \neq 0$

where π is the rate of effective hemostasis in each group.

Comparison will be performed using a Cochran-Mantel-Haenszel (CMH) test stratified by time from symptom onset to the baseline imaging scan (< 180 minutes versus \geq 180 minutes). The difference in the proportion of participants with effective hemostasis between andexanet and UC group, the corresponding 95% confidence intervals (CIs) for the difference, and the p-value for the comparison will be provided.

The analysis of efficacy will employ an alpha spending function by Lan and DeMets based on Pocock boundaries. The primary efficacy objective of the study will be considered met if the proportion of participants with effective hemostasis in the andexanet group is statistically significantly higher than that in the UC group at interim (p < 0.0310) or in the final (p < 0.0277) analysis.

3. SAMPLE SIZE DETERMINATION

Results (as of 30 Jun 2020) from the Phase 3b/4, single-arm, open-label Study ANNEXA-4 have shown that the rate of effective hemostasis is 79% (95% CI: 74% to 84%) based on evaluable participants with ICrH; the rate of effective hemostasis is 80% (95% CI of 75% to 84%) based on 340 efficacy-evaluable participants with all types of bleeding.

Based on these results, it is assumed that the rate of effective hemostasis in this study is 70% and 80% for participants treated with UC and andexanet, respectively. The 10% absolute difference represents a 33% risk reduction of not achieving effective hemostasis by andexanet as compared to UC, which is considered clinically meaningful. After accounting for early discontinuation rate and one interim analysis, it is estimated that a total sample size of approximately 900 participants (ie, 450 participants per group) will have approximately 90% power to detect a 10% absolute difference between andexanet and usual care in the rate of effective hemostasis at a 0.05 two-sided overall significance level.

4. ANALYSIS SETS

The analysis sets to be included are shown in Table 2.

-				
Analysis Set	Description			
Screened Set	All participants who signed an informed consent form.			
ES	All participants who signed an informed consent form; screen failures are excluded.			
ITT Set	All participants randomized to study intervention. Participants will be analyzed according to the study intervention they are randomized to. Participants who are randomized without signing the consent form throughout the study will not be included in the ITT Set.			
SS	All randomized participants who received at least 1 dose of the study intervention. In the usual care arm, randomized participants who received no treatment will also be part of the SS. Participants will be analyzed according to the study intervention they actually received.			
PPS	The PPS will include all participants in the ITT Set who did not have important protocol deviations that impact the primary efficacy assessment. Detailed rules on how to define the PPS are located in Section 6.1.			

Table 2:Analyses Sets

Abbreviations: ES=Enrolled Set; ITT=Intent-to-Treat; PPS=Per-Protocol Set; SS=Safety Set

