10.4. Analysis Populations

10.4.1. Safety Analysis Population

The safety analysis population will consist of all randomized patients who received the study treatment (and examet or usual care) and analyzed according to the actual treatment received.

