5.7. Safety Analyses

Safety endpoints are listed in Section 1.1. Generally, all safety analyses will be based on the Safety Set. If the study is stopped after interim analysis, safety analyses will be based on the final data cutoff unless otherwise specified.

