5.7.2. Adverse Events

AEs are defined in Protocol Section 8. An AE is any untoward medical occurrence in a clinical investigation participant administered a pharmaceutical product, regardless of causal attribution

Page 26 of 52 Alexion Confidential to study treatment or procedure. A treatment-emergent adverse event (TEAE) is any AE that occurs at any time following treatment initiation.

The number of events and the number and percentage of participants who experienced at least 1 TEAE reported through the Day 30 Follow-up Visit will be presented. TEAEs that are considered by the Investigator to be related to either the study intervention or the UC, TEAEs that lead to early withdrawals of study drug, and serious adverse events (SAEs) will be summarized in the same manner.

All SAEs and TEAEs leading to study intervention withdrawal or interruption will be listed separately.

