5.7.2.5. Deaths

The number and percentage of participants with AEs leading to death will be presented by SOC and PT as described above.

All deaths will be assessed by the EAC blinded to treatment group. Deaths occurring up to 30 days post-randomization will be referred below as 30-day death or 30-day mortality. Bleeding mortality is defined as deaths occurring within 72 hours post-randomization not associated with TEs.

All 30-day deaths, 30-day death occurring during index hospitalization, and bleeding-related mortality (defined as any death within 72 hours from randomization and not associated to the occurrence of an identified TE) will be summarized by treatment group and total based on the following causes:

- All causes
- Cardiovascular (CV) causes (resulting from myocardial infarction, sudden cardiac death, heart failure, stroke, cerebral vascular procedures, CV hemorrhage, or other)
- Non-CV causes (resulting from non-CV hemorrhage and non-CV procedure or surgery)

Time to death by all causes up to 30 days post-randomization will be analyzed using a Cox proportional hazards model adjusted for time from symptom onset to the baseline imaging scan (< 180 minutes versus \geq 180 minutes) and treatment group. Participants who did not die or discontinued prior to Day 30 will be censored at the day of the last assessment.

Page 28 of 52 Alexion Confidential Kaplan-Meier method will be used to analyze time to death with the same censoring rule. Participants who completed the study (ie, Day 30) will be censored at the day of the last assessment. Probabilities of 30-day death at different time points and median time to death will be presented by treatment group.

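### The 30-day mortality Cox model runs by default on an as-treated Safety Set, so the only modelled safety comparison is not protected by randomisation

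*SAP*

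**What the plan says.** SAP section 4, Table 2, defines the Safety Set in three steps.

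- Entry rule: "All randomized participants who received at least 1 dose of the study intervention".
- Exception for one arm: "In the usual care arm, randomized participants who received no treatment will also be part of the SS". No matching rule covers patients randomised to andexanet who are never dosed.
- Grouping: "Participants will be analyzed according to the study intervention they actually received".

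Protocol 10.4.1 likewise has the safety population "analyzed according to the actual treatment received". It is silent on patients who receive nothing.

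SAP 5.7 then states: "Generally, all safety analyses will be based on the Safety Set". SAP 5.7.2.5 falls under that section and says: "Time to death by all causes up to 30 days post-randomization will be analyzed using a Cox proportional hazards model". It adds Kaplan-Meier summaries and names no set of its own. Protocol 10.6.3 plans the same Cox model and also names no set. Neither document plans a Cox or Kaplan-Meier analysis of mortality on the ITT Set.

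**The concern.** Survival time is counted from randomisation, but a patient's presence in the analysis, and the group he or she is counted in, are settled afterwards. A patient randomised to andexanet who dies or deteriorates before dosing leaves the set. The same patient randomised to usual care stays. If the andexanet patient is given another product instead, as-treated grouping counts the patient under usual care. A usual-care patient who is given andexanet is counted under andexanet.

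The trial is open-label, so the staff who decide on dosing know the allocation, and those decisions can reflect prognosis. The documents foresee these cases. The per-protocol rules in SAP 6.1 list missing doses, procoagulant or haemostatic products given to andexanet-randomised patients who did not get andexanet within 3 hours, and andexanet given to usual-care patients. Protocol 7.2.3 and Table 5 also mention andexanet given in the usual care arm.

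What is at stake is the one safety endpoint with a specified treatment-effect model. Protocol 3.5 accepts that reversing anticoagulation raises thrombotic risk, so mortality weighs heavily in the benefit-risk judgement. Readers will expect its hazard ratio to compare the arms as randomised.

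**Working it through.** **The plan's own figures.** None is given for mortality or for the Safety Set. The only sizing statement is about 90% power for the primary endpoint with 450 per group. It reproduces: two-look power is 90.8–91.2% without dropout. It does not bear on this point, except that it supplies n = 450.

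**Inputs.**
- n = 450 per arm (SAP section 3).
- m = overall 30-day mortality, equal in both arms (no true effect). Protocol 1.0 cites rates above 30–40% for intracranial haemorrhage; 30% is used here.
- u = share of the andexanet arm never given andexanet. The documents do not state it. Assumed 2%, or 0.02 × 450 = 9 patients.
- q = mortality in those patients. Not stated either. Assumed 80–100%, with 0% as the opposite extreme.

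**Formulas.** Mortality in the remaining andexanet patients is (m − uq)/(1 − u).
- Dropped: usual care stays at m, so the difference is −u(q − m)/(1 − u).
- Moved: usual care becomes (m + uq)/(1 + u), so the difference is −2u(q − m)/(1 − u²).

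Both change sign at q = m. On the ITT Set the difference is 0 throughout. HR is taken as the ratio of log survival at day 30.

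| q | Andexanet group | Dropped: usual care, difference (HR) | Moved: usual care, difference (HR) |
|---|---|---|---|
| 80% | 0.284/0.98 = 28.98% | 30%, −1.0 points (0.96) | 0.316/1.02 = 30.98%, −2.0 points (0.92) |
| 100% | 0.280/0.98 = 28.57% | 30%, −1.4 points (0.94) | 0.320/1.02 = 31.37%, −2.8 points (0.89) |
| 0% | 0.300/0.98 = 30.61% | 30%, +0.6 points (1.02) | 0.300/1.02 = 29.41%, +1.2 points (1.05) |

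**Wider range.** With m = 30–40%, u = 1–5% and q = 60–100%, the difference is −0.2 to −3.7 points if dropped (HR 0.99 to 0.86) and −0.4 to −7.0 points if moved (HR 0.99 to 0.75). With q = 0% it is +0.3 to +2.1 points if dropped and +0.6 to +4.0 points if moved.

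**The reverse flow.** By symmetry, if 2% of the usual care arm, with 80–100% mortality, were given andexanet and regrouped, the spurious difference would be +2.0 to +2.8 points. If equal shares with equal mortality crossed in both directions, each group would return to m and the difference would be 0.

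**Against precision.** The standard error of the difference is √(2 × 0.30 × 0.70/450) = 3.1 points, so the 95% interval is about ±6.0 points. At u = 2% the shift is under half a standard error if dropped (1.4/3.1 = 0.45) and under one if moved (2.8/3.1 = 0.90).

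**The case against.** Several points on the other side stand.

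- Keeping untreated usual-care patients is right. Usual care includes no treatment (Protocol 3.1), so those patients received their assigned strategy. The gap is the missing counterpart for andexanet, combined with as-treated grouping.
- A treated set is conventional for safety tables, and the word that opens the SAP 5.7 sentence leaves room for exceptions. None is stated for mortality.
- Few patients may be affected. Protocol 3.1 rules out cross-over, allows reconstitution before randomisation and asks for dosing within 30 minutes. The eligibility criteria exclude GCS below 7 and NIHSS above 35. The illustrated shift is small against sampling error, and mortality carries no allocated alpha.
- Deaths by randomised arm will be partly visible. SAP 5.5.3 tabulates day-30 mRS by treatment group on the ITT Set, and score 6 is death. That gives counts only. The logistic model there pools death with scores 4 and 5, and no time-to-death comparison by randomised arm is planned.

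A reader might also infer that adverse events are counted over unequal windows, because a treatment-emergent event "occurs at any time following treatment initiation" and usual care may start up to 3 hours after randomisation. The documents support this only in part. SAP 6.1 starts the clock at randomisation for untreated usual-care patients. A later start would tend to undercount events under usual care, which does not flatter andexanet. Deaths and adjudicated thrombotic events are counted to 30 days from randomisation in any case. Counting all adverse events from randomisation is not a safe remedy either. Protocol 8.8 restricts reporting before treatment to serious events caused by protocol-mandated interventions, so the data may not exist.

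**Conclusion.** The point holds for the 30-day all-cause mortality Cox model. As written, it compares groups formed partly by post-randomisation events, and the plan has no version by randomised arm. With 2% of the andexanet arm undosed, 30% overall mortality and 80–100% mortality in the undosed, the spurious difference is −1.0 to −1.4 points if they are dropped and −2.0 to −2.8 points if they are moved. These are illustrations: the undosed share and its mortality are assumptions, and the documents supply neither.

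Two stronger readings are tempting but unsupported. One is that the bias must favour andexanet. That requires undosed patients to be sicker than average and ignores usual-care patients given andexanet, so the net direction is undetermined. The other is that all safety comparisons are compromised inferences. The Cox model is the only modelled one; the Kaplan-Meier output, thrombotic events and other adverse events are descriptive summaries.

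This is a cheap improvement worth making, not a flaw that invalidates the safety analysis.

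**What to change.** - In SAP 5.7.2.5, name the ITT Set, analysed by randomised arm, as the main set for the 30-day mortality Cox and Kaplan-Meier analyses. Keep the Safety Set version as supportive.
- Summarise adjudicated thrombotic events by randomised arm as well, as far as they were collected in patients who were never dosed.
- Report the number of undosed and crossed-over patients, and their deaths, by randomised arm.
- Reconcile Protocol 8.7, which starts adverse event reporting at consent, with Protocol 8.8, which restricts it before treatment starts.

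The cost is a change of SAP wording and one repeated set of tables. Deaths need no new data: Protocol 3.4 documents survival to day 30, and Protocol 10.6.3 has all deaths assessed by the blinded committee. Completeness of thrombotic events in never-dosed patients depends on how 8.7 and 8.8 are reconciled.

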5. STATISTICAL ANALYSIS

5.1. General Considerations

During the conduct of the study, the Sponsor and Investigators will be blinded to the aggregated efficacy and safety summaries. In addition, all unblinded analyses that are required to support the DSMB will be performed by an independent unblinded DSMB statistician. These analyses will be performed under the direction of the DSMB according to the analyses described the DSMB Charter. The results of these unblinded analyses will not be available to the Sponsor or Investigators until after database lock.

The safety interim analyses will follow the same procedures as the efficacy interim analysis (see Protocol Section 10.7), with the Sponsor remaining blinded to the results of these analyses unless the DSMB recommends stopping the study early.

Once the study is complete and the final database lock is performed, the study will be fully unblinded and the final analyses will be performed.

All efficacy and safety endpoint parameters will be summarized descriptively.

For continuous variables, the number of observations, mean, median, SD, first quartile, third quartile, interquartile range, and minimum and maximum values will be presented. For categorical variables, unless specified otherwise, counts and percentages will be based on the number of participants with nonmissing values in each treatment group and total. Inferential statistics will be presented only when specified.

5.1.1. Hypothesis Testing and Significance Level

For the interim analysis or the final analysis, a hierarchical testing procedure will be used to test the primary and secondary endpoints to control the overall family-wise type I error rate at 5%. At interim, the primary endpoint will be tested at a significance level of 0.0310; if the primary endpoint is statistically significant, the secondary endpoint will be tested at a significance level of 0.0310.

The same approach will be used in the final analysis with a significance level of 0.0277.

5.1.2. Coding Dictionaries

Medical history and AEs will be coded using Medical Dictionary for Regulatory Activities (MedDRA). All medications will be coded using the World Health Organization Drug Dictionary (WHODrug).

5.1.3. Statistical Software

Statistical analysis will be performed using Statistical Analysis Software (SAS) Version 9.4 (SAS Institute, Inc., Cary, NC, USA) or higher. Additional software may be used for the production of graphics and for statistical methodology not available in SAS.

5.2. Study Participants

5.2.1. Disposition of Participants

The number of participants screened and the number of screen failures, along with reason for screen failure, will be tabulated. A by-participant listing of screen failures will be provided.

The number of participants randomized to each treatment (and examet or UC) and overall (total) and the number of participants in the Safety Set, Intent-to-Treat (ITT) Set, and Per-Protocol Set (PPS), along with percentages, will be tabulated. In addition, the number of participants randomized to each treatment and total will be tabulated for the stratification factors (intended PCC use [yes versus no] and the time from symptom onset to the baseline imaging scan [< 180 minutes versus \geq 180 minutes]).

A by-participant listing showing population set status, along with randomization information, will be provided.

Enrollment by region (North America, Europe, and Asia), country, and site will be tabulated by treatment group and total.

An accounting of study participant disposition will be tabulated and will include the number and percentage of participants who completed the study (completing the 30-day Follow-up Visit for all participants) and who discontinued study early within each treatment and total, as well as the reason for discontinuation from the study. Descriptive statistics will be provided for the study duration and will be based on all participants at the time of either the interim data cutoff or the final locked dataset, as applicable.

In addition, the number and percentage of participants who fail inclusion/exclusion criteria will be tabulated by treatment group and total and will specify the protocol version under which the failure occurred.

By-participant listings tabulating participant disposition data will be provided.

5.3. Primary Endpoint Analysis

The primary objective of the study is to compare the rate of participants with effective hemostasis 12 hours post-randomization between and exanet and UC. The primary endpoint is based on the achievement of effective hemostasis, as determined by the blinded EAC based on prespecified criteria documented in the Adjudication Charter.

Effective hemostasis will be further defined as follows:

- 1 = for participants with effective hemostasis rated as excellent/good
- 0 = for participants with effective hemostasis rated as poor/none

Refer to Section 6.1, for details on how the primary efficacy endpoint is determined, including the handling of missing data.

The primary analysis will be performed on the ITT Set.

5.3.1. Estimand

Table 3 below describes the attributes of the Primary (Composite) estimand.

Page 17 of 52 Alexion Confidential

Estimand	Attributes of Estimand				
	Treatment	Endpoint	Population	Intercurrent Events Handling	Statistical Summary
Primary (composite estimand)	Andexanet vs usual care	Proportion of participants with effective hemostasis	ITT Set	Rescue medications/procedures: All participants will be considered as poor/none (not effective) for effective hemostasis if meeting Criteria 1 and/or 2 below: 1. Initiation of rescue therapies (medication or procedures) starting ≥ 3 hours post- randomization and up to < 12 hours post-	Difference in the proportion of participants with effective hemostasis between the 2 treatment groups, and its 95% confidence interval as estimated by a CMH test stratified by the time from symptom onset to baseline imaging assessment (< 180 minutes vs ≥ 180 minutes)

Table 3:Attributes of Primary (Composite) Estimand

Estimand	Attributes o	of Estimand			
	Treatment	Endpoint	Population	Intercurrent Events Handling	Statistical Summary
				change from baseline to 12 hours in hematoma volume.	
				 Core imaging laboratory request for EAC review. 	
				4. Misadministration of procoagulant blood products contrary to treatment allocation within 3 hours pos-randomization (including andexanet in usual care arm)	
				5. Performance of a surgery or interventional procedure to treat the index hematoma or that could impact hematoma volume within 3 hours post- randomization	
				Nonevaluable events : There are 2 types of reasons for nonevaluable hemostatic status:	
				 Cases deemed nonevaluable due to administrative reasons (for example, but not limited to, follow-up scan not available, not performed not 	
				performed, not interpretable, or transfer of the participant to another facility for administrative purposes)	
				 Cases deemed nonevaluable due to clinical reasons (for example, but not 	

Table 3:Attributes of Primary (Composite) Estimand

Estimand	Attributes of Estimand					
	Treatment	Endpoint	Population	Intercurrent Events Handling	Statistical Summary	
				limited to, the participant died due to index bleed or the participant had unplanned surgery draining hematoma) The decision of the EAC is considered final. The nonevaluable status due to both reasons will be treated as poor/none in the primary analysis.		

 Table 3:
 Attributes of Primary (Composite) Estimand

Abbreviations: CMH = Cochran-Mantel-Haenszel; EAC = Endpoint Adjudication Committee; ITT = Intent-to-Treat; NIHSS = National Institutes of Health Stroke Scale

5.3.2. Main Analytical Approach

Primary analysis will be performed using a CMH test stratified by time from symptom onset to the baseline imaging scan (< 180 minutes versus \geq 180 minutes). The difference in the proportion of participants with effective hemostasis, its 95% CI, and the p-value will be estimated.

A by-participant listing of effective hemostasis will be provided.

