3.2. Blinding and Randomization

3.2.1. Randomization

This study will be randomized 1:1 and exanet to usual care, stratified by:

- Intended-usual-care-agent; and
- Time from symptom onset to baseline imaging scan (< 180 minutes vs ≥ 180 minutes).

To account for potential differences in the demographics or baseline severity of patients who receive Prothrombin Complex Concentrate (PCC) products (e.g., KCentra[®]) or recombinant factor VIIa (rfVIIa) (e.g., NovoSeven[®]), anti-inhibitor coagulant complex (e.g., FEIBA[®]), or other plasma-derived coagulation factor concentrates, or a regional difference in the use of these agents, randomization will be stratified by an intended-usual-care-agent (plasma-derived coagulation factor concentrates vs. other) determined on a patient-by-patient basis. The intended-usual-care-agent is determined by the Investigator and is the Investigator's best determination of what type of therapy will be used for the patient, in the event that the patient is randomized to the usual care arm. In addition, to account for potential imbalances between treatment groups in baseline factors known to be predictive of hematoma expansion, randomization will also be stratified by the time from symptom onset to baseline imaging scan (< 180 minutes vs \geq 180 minutes). The randomization scheme will be generated by the Sponsor.

3.2.2. Blinding

To avoid bias, the study treatment assignment and anti-fXa activity levels will be blinded to the independent EAC and the Imaging Core Laboratory. However, because of the many therapeutic options available to Investigators to treat patients randomized to usual care, it is considered unfeasible to blind all study personnel (especially those directly involved in the care of an enrolled patient) to treatment assignment. Thus, the study treatment allocation of each patient will be unblinded to the local Investigator and most of the local site study team. However, to perform neurologic assessments to support efficacy endpoints (particularly NIHSS and Glasgow Coma Scale [GCS]) at 12- and 24-hours following randomization, individuals at each site who are tasked with these assessments at these time-points will be blinded. Furthermore, the Sponsor will remain blinded to adjudication outcomes, post-randomization anti-fXa activities, and imaging results. Blinding processes and procedures are outlined in a separate Blinding Plan.

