10.5.4.2. Primary Efficacy Endpoint Analysis

The primary objective of the study is to compare the proportion of patients with effective hemostasis (excellent or good as adjudicated by the blinded EAC) between and exanet and usual care. The following hypothesis will be evaluated:

Ho: $\pi_{UC} - \pi_{andexanet} = 0$ HA: $\pi_{UC} - \pi_{andexanet} \neq 0$

Analysis will be performed using a Cochran-Mantel Haenszel (CMH) test stratified by time from symptom onset to baseline imaging scan (< 180 minutes vs. \geq 180 minutes). The corresponding 95% confidence intervals (CIs) for the difference in proportions, and the proportions from the two groups, will be provided.

The study will be considered to meet its primary efficacy objective if the proportion of and exanet-treated patients with effective hemostasis (excellent or good as adjudicated by the independent EAC) is significantly higher (p < 0.031 at the interim analysis, OR p<0.0277 at the final analysis) than the proportion of patients with effective hemostasis randomized to usual care.

A sensitivity analysis will be performed using a CMH test stratified by intended-usual-care-agent and time from symptom onset to baseline imaging scan.

Further details of the primary analysis will be provided in the SAP.

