The shift parameter will take a series of values; for each value, the imputation will be applied to generate 100 datasets, and the same stratified CMH method as described in Section 5.3.1 will be used to compare andexanet and UC. Rubin's rule (Rubin, 1967) will be applied to combine results.

At the end of this process, a plot for the p-values with the shift parameter values will be generated to evaluate the impact of missing data imputation to the statistical comparison.

Sensitivity analysis 5: The primary endpoint will be analyzed by a CMH method with a 5-stratum stratification factor. The 5 strata are:

- Participants enrolled prior to Protocol Amendment V1 who were randomized not by stratifying intended PCC use (yes versus no)
- Participants enrolled after Protocol Amendment V1, and with intended PCC use and the time from symptom onset to baseline imaging assessment < 180 minutes
- Participants enrolled after Protocol Amendment V1, and with intended PCC use and the time from symptom onset to baseline imaging assessment ≥ 180 minutes
- Participants enrolled after Protocol Amendment V1, and with no intended PCC use and the time from symptom onset to baseline imaging assessment < 180 minutes
- Participants enrolled after Protocol Amendment V1, and with no intended PCC use and the time from symptom onset to baseline imaging assessment \geq 180 minutes

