5.9.1. Stopping Criterion Due to Efficacy at Interim

The overall type I error for the interim and final analyses is controlled at 5% by employing the alpha spending function by Lan and DeMets based on Pocock boundaries (DeMets, 1994). If the interim p-value is < 0.0310 for comparing and exanet and UC in the primary endpoint analysis, DSMB may recommend stopping the study. In this case, the efficacy results from the interim analysis (with 50% of the anticipated participants) will be used for regulatory communication and submission. Enrollment of participants will proceed without interruption while the analysis is ongoing, resulting in > 50% of the anticipated participants in the final data cutoff; efficacy analysis on the final data cutoff will be considered as a sensitivity analysis.

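### The primary CMH test leaves out intended usual-care agent, a randomisation stratum since Amendment 1: a small efficiency loss if that factor predicts hemostasis, and free to recover

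*SAP*

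**What the plan says.** Protocol 3.2.1 names two stratification factors: onset-to-scan time (under or at least 180 minutes) and the agent the investigator would use if the patient were allocated to usual care. On the second it says "randomization will be stratified by an intended-usual-care-agent", because users of factor concentrates may differ in demographics or severity, or because use may vary by region.

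The primary test keeps only the first factor. SAP 5.3.2: "Primary analysis will be performed using a CMH test stratified by time from symptom onset to the baseline imaging scan". SAP 2, the estimand table in SAP 5.3.1 and Protocol 10.5.4.2 agree.

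Two pre-specified sensitivity analyses bring the second factor back:
- Protocol 10.5.4.2: "A sensitivity analysis will be performed using a CMH test stratified by intended-usual-care-agent and time from symptom onset". This is sensitivity analysis 1 in SAP 5.3.3, which excludes patients without data on intended PCC use.
- Sensitivity analysis 5 in SAP 5.3.3: "The primary endpoint will be analyzed by a CMH method with a 5-stratum stratification factor". One stratum holds the pre-Amendment-1 patients; the other four cross intended PCC use with time for later patients.

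The SAP version history records the change to one factor at version 1.0. It gives a single reason for the whole list of changes: alignment with Amendment 3 and regulatory comments. The protocol's overview of changes records the removal under Amendment 3 without a reason.

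**The concern.** Stratified randomisation balances the arms on the factor, so the true variance of the treatment difference contains only within-stratum variation. A test that ignores the factor still charges the between-stratum variation to error. If the factor is prognostic, the standard error is too large, the test rejects less often than its nominal level under the null, and some power is given up.

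The sponsor considered the factor potentially important enough to constrain randomisation. The interim test is where the loss would be largest, and SAP 1.2 and 5.9.1 allow the interim data to become the confirmatory efficacy analysis.

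**Working it through.** **Inputs from the documents.** Overall level: "at a 0.05 two-sided overall significance level". Looks: "At interim, the primary endpoint will be tested at a significance level of 0.0310" and "The same approach will be used in the final analysis with a significance level of 0.0277", obtained by "employing the alpha spending function by Lan and DeMets based on Pocock boundaries". Rates 70% and 80%, 450 per group, power about 90% (SAP 3). An early-discontinuation allowance is mentioned without a figure.

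**Reproducing the plan's figures.** Pocock-type spending at half information is 0.05 × ln(1 + (e − 1) × 0.5) = 0.0310. With correlation √0.5 between looks, the final two-sided level is 0.0277. The rounded pair gives an overall error of 0.04997. Power at 450 per arm is 89.8% for one test at 0.0277, and 90.8% (pooled variance) to 91.2% (unpooled) over both looks. With 437 per arm (about 3% lost) it is 89.9-90.3%. The design figures stand.

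**Assumptions not in the documents.** q is the share intended for PCC (50%, 70%, 85%). g is the gap in success rate between the two agent strata (0 to 20 points).

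**True size.** With marginal rate p, the ratio of within-stratum to total variance is V = 1 − q(1 − q)g² / [p(1 − p)]. Under the null, p = 0.70. The true size of the nominal 0.0277 test (critical value 2.201) is 2[1 − Φ(2.201/√V)].
- q = 0.5, g = 0.10: V = 1 − 0.25 × 0.01/0.21 = 0.9881, size 0.0268.
- q = 0.5, g = 0.20: V = 1 − 0.25 × 0.04/0.21 = 0.9524, size 0.0241.

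**Two-look power.** The test statistic uses a standard error built on p = 0.75, without the factor (time-only) or with it. The true standard error uses within-stratum variances at 70% and 80%. For q = 0.5, g = 0.20, these are √(2 × 0.1875/450) = 0.0289 time-only, √(2 × 0.1775/450) = 0.0281 with the factor, and √((0.20 + 0.15)/450) = 0.0279 true.

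| q | g (points) | V | Size of 0.0277 test | Overall type I error, time-only | Power time-only | Power with factor | Gain (points, unrounded) |
|---|---|---|---|---|---|---|---|
| any | 0 | 1.0000 | 0.0277 | 0.0500 | 90.91% | 90.91% | 0 |
| 50% | 5 | 0.9970 | 0.0275 | 0.0496 | 90.94% | 91.01% | 0.06 |
| 50% | 10 | 0.9881 | 0.0268 | 0.0484 | 91.04% | 91.29% | 0.25 |
| 50% | 20 | 0.9524 | 0.0241 | 0.0438 | 91.43% | 92.38% | 0.95 |
| 70% | 10 | 0.9900 | 0.0269 | 0.0486 | 91.02% | 91.23% | 0.21 |
| 70% | 20 | 0.9600 | 0.0246 | 0.0448 | 91.35% | 92.15% | 0.80 |
| 85% | 10 | 0.9939 | 0.0272 | 0.0492 | 90.98% | 91.10% | 0.13 |
| 85% | 20 | 0.9757 | 0.0258 | 0.0468 | 91.18% | 91.67% | 0.49 |

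**Simulation check** (CMH, two time strata against four strata, 40,000 trials per scenario).
- Final test, N = 900, q = 50%, g = 20: type I error 0.0237 against 0.0272; power 91.0% against 91.9%.
- Interim test, N = 450 at 0.0310, q = 50%: power 62.5% against 63.1% at g = 10, and 62.7% against 65.0% at g = 20.
- Interim test with 10% of patients (assumed) in a fifth, pre-Amendment-1 stratum, q = 50%: 62.4% against 62.2% at g = 0, 62.2% for both at g = 5, and 62.7% against 64.7% at g = 20.

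**The case against.** The strongest defence is that the one-factor test is a valid, deliberate choice, stated consistently in both documents, with both two-factor versions already pre-specified. The error runs only towards conservatism, the cost is small over any range examined, and nobody has shown that intended agent is prognostic: Protocol 3.2.1 speaks only of potential differences. Most of this stands, and it limits the point to a minor one.

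Three parts do not settle the matter.
- A documented change is not a stated rationale. The reason in the version history covers a whole list of changes and does not say that a regulator asked for this one.
- Missing stratification in early patients does not separate the two factors. The protocol's overview of changes says Amendment 1 added both, yet time was kept.
- Sensitivity analysis 1 is not a full-ITT alternative, because it excludes patients without the data.

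One objection to adopting sensitivity analysis 5 as it stands is fair. It pools pre-Amendment-1 patients and so loses their time split, which the present primary test keeps. Those patients enrolled early, so their share is largest at the interim.

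A reader might infer that the confirmatory test definitely runs below its level. The documents do not support that, because it depends on a prognostic effect they do not quantify. Nor do they support assuming a gap beyond 20 points to enlarge the loss. With 70% PCC-intended, marginal rates held at 70% and 80%, and the PCC-intended stratum the worse one, a 30-point gap would need 80% + 0.7 × 30 = 101% success in the other stratum on andexanet.

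**Conclusion.** The primary CMH omits a factor used in randomisation since Amendment 1, and no specific reason is given. This is a minor efficiency point and a free improvement.

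If 50-70% of patients are PCC-intended and success rates differ by 10-20 points between the agent strata (both assumed), the 0.0277 test has true size of about 0.027-0.024. The overall power cost is about 0.2-1 point (0.13 at 85% prevalence and a 10-point gap), and the interim cost is at most about 2.3 points. At a 5-point gap the overall cost is under 0.1 point, and at zero it is nil.

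The omission does not threaten validity or leave the trial underpowered. Type I error is never inflated, and time-only two-look power is 90.9-91.4% at 450 per arm throughout the table, which meets the stated figure of about 90%. Whether intended agent would help the secondary ANCOVA or the other models is not quantified here.

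**What to change.** Before the interim data are unblinded:
- Make the primary CMH stratified by onset-to-scan time crossed with intended agent as recorded at randomisation, with a 'not collected' level for pre-Amendment-1 patients. This keeps every ITT patient and the time split. The 5-stratum CMH of sensitivity analysis 5 is an acceptable alternative if its loss of the early patients' time split is accepted.
- Keep the time-only CMH as a sensitivity analysis.
- Use the same strata for the stage-wise statistics in SAP 5.9.3.
- Use one label and definition for the stratum. Protocol 3.2.1 contrasts plasma-derived coagulation factor concentrates with other treatment; SAP 1.2 and 5.3.3 use intended PCC use, yes or no.

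If the sponsor prefers one factor, a sentence giving the specific reason would do instead. Adding the factor to the secondary ANCOVA and other models is optional. The cost is wording in SAP 2, 5.3 and 5.9.3 and in the protocol synopsis and Section 10.5.4.2; no new data are needed.
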